7.2.11 Other Safety Parameters

Best Corrected Distance Visual Acuity

For additional safety variables associated to BCDVA assessment please refer to section 7.2.9.

External Ocular Examination

External Ocular Examination assesses the motility of the extraocular muscles and the appearance and function of the eyelids before the instillation of any dilating or anesthetic eye drops.

Motility of extraocular muscle and appearance/function of eye lids is assessed separately for each eye at each Study Visit and is recorded on the eCRF pages ‘External Ocular Examination’ and ‘Appearance and Function of Eyelids’.

For the analysis, the motility of the extraocular muscle will be evaluated by the field of movements Right and up (‘Normal’, ‘Abnormal’), Right (‘Normal’, ‘Abnormal’), Right and Down (‘Normal’, ‘Abnormal’), Left and Up (‘Normal’, ‘Abnormal’), Left (‘Normal’, ‘Abnormal’), Left and Down (‘Normal’, ‘Abnormal’) as documented at the eCRF. No imputation will be envisaged for these parameters.

Appearance and function of eyelids will be summarized by the following parameters:

- Incidence of proven eyelid deformity/abnormality, which will be considered as present, if the question ‘Evidence of eyelid deformity or abnormality’ on the eCRF page ‘Appearance and Function of Eyelids’ is answered ‘Yes’.
- Incidence of abnormal motor function of eyelids (i.e. upper lid elevation and forceful lid closure), which will be considered as present, if the question ‘Motor function of eyelids’ on the eCRF page ‘Appearance and Function of Eyelids’ is answered ‘ABNORMAL’.
- Incidence of corneal exposure in case of closed eyelids, which will be considered as present, if the question ‘Is there corneal exposure when the eyelids are closed?’ on the eCRF page ‘Appearance and Function of Eyelids’ is answered ‘Yes’.
- Incidence of proven punctal occlusion, which will be considered as present, if the question ‘Is there evidence of punctal occlusion?’ on the eCRF page ‘Appearance and Function of Eyelids’ is answered ‘Yes’.
- Incidence of punctal plugs, which will be considered as present, if the box ‘Punctal plugs’ is ticked on the eCRF page ‘Appearance and Function of Eyelids’.
- Incidence of thermal or surgical occlusion, which will be considered as present, if the box ‘Thermal or surgical occlusion’ is ticked on the eCRF page ‘Appearance and Function of Eyelids’.
- Incidence of Other punctal occlusion, which will be considered as present, if the respective ‘Other’ box is ticked on the eCRF page ‘Appearance and Function of Eyelids’.

Slit Lamp Examination

Slit lamp examination is performed separately for each eye at each Study Visit and is recorded on the eCRF page ‘Slit Lamp Examination (Biomicroscopy)’.

The following assessments will be performed:

Eye Structure	Rating
---------------	--------

Eye Structure	Rating
Eye Lids	1 = None (normal) 2 = Mild (redness localized to a small region of the lid(s) margin OR skin) 3 = Moderate (redness of most of all of lid margin OR skin) 4 = Severe (redness of most or all of lid margin AND skin) 5 = Very Severe (marked diffuse redness of both the lid margin AND skin)
Lashes	1 = Normal 2 = Abnormal (specify)
Conjunctiva	1 = None 2 = Mild 3 = Moderate 4 = Severe
Cornea	1 = Normal 2 = Abnormal
Lens	1 = No Opacification (normal lens) 2 = Mild Lens Opacification 3 = Moderate Lens Opacification 4 = Severe Lens Opacification 5 = Cataract Extraction with Intraocular Lens Implant In addition there is also a field to specify Other findings
Iris	1 = Normal 2 = Abnormal
Anterior Chamber Inflammation	1 = None (no Tyndall Effect) 2 = Mild (Tyndall Effect barely discernable) 3 = Moderate (Tyndall beam in the anterior chamber is moderately intense) 4 = Severe (Tyndall beam in the anterior chamber is severely intense)
Other	Specification and assessment of other investigated eye structure

For each eye structure, the investigator will have the opportunity to tick also ‘Not done/Not evaluable’, which will be treated as ‘Missing’ for analysis purposes.

All grading assessments of different eye structures will be evaluated as collected on the eCRF. No imputation will be envisaged for these parameters.

No aggregated presentation is planned for other assessments done during Slit lamp evaluation.

Intraocular Pressure (IOP)

Intraocular Pressure testing will be performed using Goldmann Tonometer and the resulting value (mmHg, format 4.1) is recorded on the eCRF page ‘Intraocular Pressure’. The change from baseline will be calculated as differences from Baseline.

Dilated Fundus Ophthalmoscopy

Fundus ophthalmoscopy to assess the eye structure will be performed and results recorded on the eCRF page ‘Fundus Ophthalmoscopy’ by utilizing the following assessments.

Eye Structure	Rating
Vitreous	1 = Normal 2 = Abnormal (specify) 3 = Not done/Non-Evaluable
Retina / Macula	1 = Normal 2 = Abnormal (specify) 3 = Not done/Non-Evaluable
Choroid	1 = Normal 2 = Abnormal (specify) 3 = Not done/Non-Evaluable
Optic Nerve	1 = Normal 2 = Abnormal (specify) 3 = Not done/Non-Evaluable
Cup/Disc Ratio	1 = Normal 2 = Abnormal (specify) 3 = Not done/Non-Evaluable For abnormal values the Cup/Disc Ratio will be included in the ‘Specify’ field.

All grading assessments of different eye structures will be evaluated as collected on the eCRF. No imputation will be envisaged for these parameters. Information on Cup/Disc Ratio will be listed only, as no investigator assessment on abnormality was performed.

No aggregated presentation is planned for recorded details.

8 Analysis Methods

8.1 General Methods

For the study, both eyes are under investigation. For analysis purposes all eye-related assessments will be displayed separately by Primary/Secondary Eye. Untreated eyes will not be considered for analysis and be listed only indicated with 'Untreated'.

For continuous variables, the mean, standard deviation, minimum, median and maximum will be presented by treatment group, together with the total number of observations and the number of missing and non-missing values. Unless otherwise specified minimum and maximum values will be reported to the same number of decimal places as the recorded measurements, mean and median are reported to one more decimal place and standard deviation one additional decimal place more than the mean.

For categorical variables, absolute and relative frequencies will be reported by treatment group. Relative frequencies will be based on all observations and reported as a percentages to one decimal place. Unless otherwise specified, percentages will be based on the number of patients with data in the considered analysis set and will not be calculated for missing categories.

Incidences over a specific time interval like adverse events, medical history and concomitant medication will be reported on a patient basis. The percentages will be calculated using the number of patients in the treatment group for the considered analysis set as denominator. For the presentation of incidences during the Follow-Up Period, the SAF-F set will be used, which results in a reduction of the denominator to the number of patients in the SAF, who have entered the Follow-Up Period.

All hypotheses will be tested at a 5% level of significance using a two-sided test.

P-values will be rounded to three decimal places. If a p-value is less than 0.001 it will be reported as "<0.001." If a p-value is greater than 0.999 it will be reported as ">0.999.

Statistical significance will be declared if the rounded p-value will be less than 0.050 unless stated otherwise. Two-sided 95% confidence intervals of the differences between the treatment groups will be calculated as indicated in sections 8.2 and 8.3.

Post-Text TLFs will be provided in collated electronic MS Word .rtf files (i.e. table columns and rows appear as free text instead of MS Word Table format).

8.2 Specific Methods for Primary Safety and Tolerability Analyses

All primary safety and tolerability analyses will be performed on the SAF.

Generally, the analysis of the Primary Eye will be considered as the primary result, whereas the analyses in Secondary Eye will be considered as supportive.

No statistical inference is foreseen for the analyses of primary safety outcomes.

For the VAS Tolerability Scores, the change from baseline in the respective score will be compared between treatment groups in an explorative manner per Eye and Visit.

The null hypothesis will be tested that there is no difference between rhNGF and Vehicle in the mean overall change from baseline between both treatments with respect to evaluated score:

$$H_0: \mu_{\text{rhNGF}} = \mu_{\text{Vehicle}}$$

$$H_1: \mu_{\text{rhNGF}} \neq \mu_{\text{Vehicle}}$$

Where μ is the mean change from baseline at considered visit within the given treatment group. This hypothesis will be tested with an Analysis of the Covariance (ANCOVA) with treatment and respective baseline value in the model.

The Least-squares means estimate of the treatment effect and the treatment group difference (both with 95% confidence intervals) will be reported. The analysis will be performed in the SAF.

These analyses will be performed for the Overall Tolerability Score as well as for all subscores per eye for the Week 1, Week 4 and Week 8 visits.

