11.5.4. Safety Analysis

Safety variables will be presented for the Safety population.

The primary safety endpoint in this study is Adverse Events (AEs). AEs will be recorded at the scheduled study visits and may also be recorded at any unscheduled visit that occurs during the study.

AEs will be presented, by treatment group, in terms of the incidence, severity and relationship to the study drug, overall and by SOC (System Organ Class) and preferred term. Serious AEs (SAEs) will be presented in the same way. All adverse events will be reported by MedDRA preferred term.

The following adverse event summary tables and listings will be provided:

Tables:

- Frequency and Incidence of Subjects with Adverse Events
- Frequency and Incidence of Subjects Discontinued Due to Adverse Events
- Frequency and Incidence of Subjects with Serious Adverse Events
- Adverse Events by Coded Adverse Event and SOC
- Overall Frequency and Incidence of Adverse Events
- Overall Frequency and Incidence of Adverse Events by Severity
- Overall Frequency and Incidence of Treatment-Related Adverse Events
- Overall Frequency and Incidence of Adverse Events Occurring at Rates Greater Than or Equal to 1.0%
- Overall Frequency and Incidence of Adverse Events by Age

Listings:

- Concomitant Diseases and Medications for Subjects with Adverse Events by Investigator and by Subject
- Coded and Descriptive Terms of Adverse Events by Investigator and by Subject
- Deaths, Other Serious or Clinically Significant Adverse Events
- Adverse Events by Investigator and by Subject

In addition to reporting of adverse events for any untoward (unfavorable and unintended) medical occurrences, adverse events will also be reported for any clinically relevant change from baseline in any assessment evaluated during the study, based upon an assessment by the Investigator.

Ocular tolerability as measured by the VAS will be analyzed by means of analysis of variance, including terms for treatment, time, and treatment by time interaction.

Best corrected distance visual acuity, external ocular examination, slit lamp examination, intraocular pressure, and dilated fundus ophthalmoscopy, will be presented with the appropriate descriptive statistics and shift tables will be used to present shifts from before and after treatment at each recording time points.

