3.4 Primary and Secondary Outcomes

The primary objective is to evaluate the safety and tolerability of rhNGF vs Vehicle.

The primary safety outcomes of the study are:

- *Unexpectedly severe progression of optic neuropathy as measured by central vision loss, by visual field testing, or by examination of the optic nerve*
- *Intolerance or allergy to the drug*
- *Adverse events affecting ocular function or eye pressure, which differ from those expected in the course of glaucoma, which are thought to be potentially related to the drug*
- *Local or systemic toxicities considered serious adverse events that are potentially related to the drug*

The primary tolerability outcome of the study are:

- Outcome from Ocular tolerability questionnaire using visual analogue scales (VAS)

Exploratory secondary efficacy outcomes based on functional and structural assessments of the study are:

- Change in BCDVA
- Changes in visual field using perimetry
- Changes in ERG including pattern ERG
- Changes in ganglion cell layer and nerve fiber layer thickness measured by optical coherence tomography (OCT)
- Changes in mitochondrial redox potential (not considered in this SAP)

Details for all specified primary and secondary outcomes are provided in section 7.2 of the SAP.

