The following refinements of the pre-planned analysis in the study protocol were implemented in this SAP:

- The study protocol defines the Safety Set as all treated patients. However, the Safety Set will serve a primary analysis cohort for the primary study objectives. To ensure formal maintenance of randomization, the Safety Set will be refined to “all randomized patients who received at least one study treatment”. It is notable, that randomization and dispensation of first study medication are both performed at site within one process. So, it is not expected that a patient would be treated without being randomized.
- Study protocol section 11.5.4 provides specifications of tables and listings for displaying documented AEs. This presentation of data will be aligned to data presentation of other studies investigating rhNGF to facilitate data interpretation. This change is purely organizational without omitting any data presentation described in the study protocol with one exception: due to the relative few numbers of patients, no separate listing of concomitant disease and medications will be provided for patients with adverse events.

4 General Definitions

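### The SAP replaces the protocol's single VAS tolerability model with separate per-visit ANCOVAs without declaring it, and leaves no across-visit comparison for the primary tolerability outcome

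*SAP*

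**What the plan says.** **Protocol.** Section 11.5.4 says that the VAS "will be analyzed by means of analysis of variance, including terms for treatment, time, and treatment by time interaction". It names no subject effect, covariance structure or baseline term. Section 11.5.1 says that changes in the analyses will be reported and justified in the SAP.

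**SAP, status of the outcome.** Section 3.4 gives the VAS questionnaire as the primary tolerability outcome.

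**SAP, model.** Under section 8.2, change from baseline is "compared between treatment groups in an explorative manner per Eye and Visit". The null hypothesis is introduced as concerning the overall mean change, but μ "is the mean change from baseline at considered visit within the given treatment group". Then: "This hypothesis will be tested with an Analysis of the Covariance (ANCOVA) with treatment and respective baseline value in the model". This is done at Weeks 1, 4 and 8, for the overall score and each of seven symptom scores, in each eye.

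**SAP, list of changes.** Section 3.6 covers mitochondrial redox potential, ERG and visual field. Under "The following refinements of the pre-planned analysis in the study protocol were implemented in this SAP" it then gives two items: the Safety Set definition and the adverse event displays. The VAS model is in neither list.

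**SAP, related rules.** Section 8.4.1 says no covariate adjustment is planned. Section 8.4.2 uses observed data without imputation. Under section 7.1, a patient who leaves during treatment has the Week 8 procedures at exit, and that visit is assigned to Week 1, 4 or 8 by window.

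**The concern.** The change affects the outcome that carries the tolerability objective, and a reader who relies on section 3.6 would not learn of it. It also removes content. The protocol's terms give a treatment comparison over the whole treatment period and a test of whether the difference changes with time. The SAP's separate fits give neither.

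There is a secondary cost in estimation. In an eye-drop trial, patients who record more discomfort may be more likely to stop. A separate analysis at a later visit cannot use the earlier scores of those who have left, so it can understate discomfort on active drug. With 20 vehicle patients and no formal sample size calculation, the precision lost by never combining the three visits also matters.

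**Working it through.** **1. The two plans side by side**

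| | Protocol 11.5.4 | SAP 8.2 |
|---|---|---|
| Model | one analysis of variance | separate ANCOVA per score, eye and visit |
| Time and interaction terms | yes | no |
| Baseline term | not stated | yes |
| Subject effect or covariance | not stated | not needed (one visit per fit) |
| Across-visit difference | available | none |
| Declared in SAP 3.6 | – | no |

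The SAP yields 8 scores × 3 visits × 2 eyes = 48 visit-wise tests and no summary over the treatment period. Limiting inference to Weeks 1–8 is consistent with protocol 11.5.1, which plans no formal testing in follow-up.

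**2. Internal conflicts in the SAP.** The null in 8.2 is worded for an overall change, but μ is visit-specific. Section 8.4.1 rules out covariates, but 8.2 includes baseline.

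**3. What happens to early leavers.** They stay in the ANCOVA of every visit they attended. Their exit VAS is used if it falls in a window in SAP Table 2: days 5–9, 24–32 or 49–63 after first dose.
- Days covered: 5 + 9 + 15 = 29 of days 1–63.
- Days not covered: 1–4, 10–23 and 33–48, which is 4 + 14 + 16 = 34. An exit on these days has no mapped visit.
- A leaver adds nothing to visits after the mapped one.

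**4. Precision, complete data.** Assume 40:20, equal correlation ρ between all visits including baseline, and SD 1.
- Single-visit ANCOVA: SE = √[(1 − ρ²)(1/40 + 1/20)]
- Baseline-adjusted mean of three visits: SE = √[((1 + 2ρ)/3 − ρ²)(1/40 + 1/20)]

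| ρ | single visit | mean of three | ratio |
|---|---|---|---|
| 0.3 | 0.261 | 0.182 | 0.70 |
| 0.5 | 0.237 | 0.177 | 0.75 |
| 0.7 | 0.196 | 0.152 | 0.78 |
| 0.9 | 0.119 | 0.096 | 0.81 |

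The gain comes from averaging over visits.

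**5. Bias under discomfort-driven dropout.** The documents give no SD, effect size, correlation or dropout rate, so every input except the 40:20 split is assumed: SD 15 mm, correlation 0.6 (baseline included), true difference 8 mm at each visit, normal scores with mean 0 before treatment. Half of the patients above 20 mm leave before the next visit, and exit-visit data are ignored. Simulated dropout is about 18% on active and 8% on vehicle.

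| Week 8 estimate | mean | shortfall |
|---|---|---|
| SAP's baseline-adjusted ANCOVA | 7.4 mm | (8 − 7.4)/8 ≈ 7% |
| Likelihood-based repeated-measures model | about 8.0 mm | about 0 |

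The standard error is 3.45 mm for the Week 8 ANCOVA and 2.58 mm for the three-visit average. The ratio is 2.58/3.45 = 0.75, so about 25% smaller.

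Sensitivity of the ANCOVA estimate: 5–7% low for correlation 0.4–0.8; 7.8 mm with half the leaving probability (10% and 4% dropout); 6.9 mm if baseline is uncorrelated with later visits.

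**The case against.** Three stronger readings are tempting, and the documents support none of them.

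*That the protocol promised a repeated-measures analysis.* It says only "analyzed by means of analysis of variance, including terms for treatment, time, and treatment by time interaction". Fitted literally, with no subject term, that model would have a type I error for treatment of about 0.12, 0.17 and 0.21 at correlations 0.3, 0.5 and 0.7. A classical complete-case repeated-measures ANOVA would exclude early leavers altogether. Against either version the SAP's ANCOVA is arguably safer. A mixed model completes the protocol's terms; it does not restore a model the protocol specified.

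*That the SAP drops early leavers.* It does not (working, step 3). They are lost only to later visits, or when the exit falls between windows.

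*That the Week 8 difference would be understated by about 16%.* In the same scenario that is an unadjusted completer comparison: 6.7 mm, (8 − 6.7)/8 ≈ 16%. The SAP adjusts for baseline, which brings the shortfall to about 7%, or 0.6 mm against a standard error of 3.45 mm.

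It is also fair to say that the comparison is labelled explorative, that no confirmatory decision rests on it, and that visit-specific differences are a legitimate tolerability question. VAS summaries by visit, intolerance counts and withdrawals due to adverse events will be reported on the Safety Set, so discomfort-driven dropout stays visible. All this limits the consequences. It does not explain the omission from section 3.6 or the loss of any overall comparison.

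**Conclusion.** The point holds as a reporting gap and a missed, inexpensive improvement. Three things follow from the text alone: the model changed, the change is undeclared, and no across-visit difference or treatment-by-time test remains. The two wording conflicts (overall against visit-specific mean; covariate adjustment) are equally plain.

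The numerical effect is modest and rests on assumed inputs. The bias of about 7% at Week 8 depends on the dropout mechanism, on the correlation with baseline, on ignoring exit-visit scores, and on normal scores standing in for a bounded 0–100 scale. The standard error reduction of about 25% (19–30% with complete data, for correlations 0.9 to 0.3) compares a three-visit average with a single visit. These are different quantities, equal only if the treatment difference is constant over time, which is why both should be reported.

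**What to change.** 1. In SAP 8.2, for each score and eye, fit one mixed model for repeated measures to the Week 1, 4 and 8 changes: baseline VAS, treatment, visit, treatment-by-visit, unstructured within-patient covariance. Report the averaged difference and each visit's difference with 95% CIs, and the interaction test.
2. In SAP 3.6, declare and justify the departure from protocol 11.5.4. This is needed even if the per-visit ANCOVAs are kept.
3. In 8.2, make the null hypothesis and the definition of μ agree. In 8.4.1, acknowledge the baseline term.
4. In 7.1, state how an exit VAS that falls between windows is assigned.

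The cost is SAP wording, a little more programming with a standard procedure, and a covariance assumption that must be stated. With three visits, unstructured means 3 variances and 3 covariances. No new data are needed, and visit-specific differences are still reported.

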8.3 Specific Methods for Exploratory Efficacy Analyses

Generally, the analysis of the Primary Eye will be considered as the primary result, whereas the analyses in Secondary Eye will be considered as supportive. Exploratory efficacy analysis will be performed on the ITT.

A similar analysis as foreseen for VAS tolerability scores (see section 8.2) will be performed for exploratory efficacy outcomes at Week 8. This comprises the following inferential analyses:

- Change from Baseline in Visual Acuity Score at Week 8
- Change from Baseline in LogMAR at Week 8
- Change from Baseline in PhNR at Week 8
- Change from Baseline in Average RNFL Thickness, all single quadrants and clock hours at Week 8
- Changes from Baseline in Macular Thickness at Week 8 for all respective areas
- Changes from Baseline in Macular Cube Thickness at Week 8 for all respective areas

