11. ANALYSIS PLAN

The primary objective of the study is to assess the safety and tolerability of a 180µg/ml TID dose regimen of recombinant human nerve growth factor (rhNGF) eye drop solution administered over 8 weeks versus a vehicle control in patients with progressive primary open-angle glaucoma despite IOP control.

The secondary objectives are to measure the changes in BCDVA, visual field, ERG and structural changes in changes in ganglion cell layer and nerve fiber layer thickness measured by optical coherence tomography. The secondary outcomes will be examined at 1, 4 and 8 weeks of therapy, and at 4 and 24 weeks after cessation of therapy (Week 12 visit and Week 32 visit), and will include functional assessments to investigate evidence of a persistent biological effect after discontinuation of the study treatment.

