11.5. STATISTICAL ANALYSIS

Data base will be locked after all patients have completed their Week 12 Visit and main objectives analysis will be performed on unmasked data. At the end of the study (i.e. after all patients have completed Week 32 Visit), an updated analysis will be performed presenting the complete study data. All analysis will be detailed in a statistical analysis plan (SAP). All exploratory efficacy variables will be tabulated with the appropriate descriptive statistics at the 0, 4, 8, 12 and 32 weeks timepoints and appropriate inferential tests with 95% confidence limits of the difference between treatments will be produced.

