11.5.1. General Principles

All patient data collected on the eCRF will be listed by patient, treatment group and center.

Appropriate descriptive statistics will be produced, according to the variable. For continuous data the mean, standard deviation, median and range (minimum and maximum) will be presented. For categorical data, frequencies and percentages will be presented. If appropriate, 95% confidence intervals around the mean or the proportions will be presented.

In tabulations, denominators for calculation of percentages will be taken as the number of non-missing responses in the specified analysis population and treatment group unless otherwise stated.

Unless otherwise specified, the significance level used for statistical testing will be 5% and two-sided tests will be used.

All variables recorded in the follow-up period will be presented using appropriate descriptive statistics, and no formal statistical testing will be performed.

Full details of all planned data summaries and analyses, with any changes in analyses as detailed below will be reported and justified in the Statistical Analysis Plan (SAP).

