3.1 Study Objectives

The primary objective of the study is to assess the safety and tolerability of a 180µg/ml TID dose regimen of recombinant human nerve growth factor (rhNGF) eye drop solution administered over 8 weeks versus a vehicle control in patients with progressive primary open-angle glaucoma despite IOP control.

The secondary objectives are to measure the changes in BCDVA, visual field, ERG and structural changes in changes in ganglion cell layer and nerve fiber layer thickness measured by optical coherence tomography. The secondary outcomes will include functional assessments to investigate evidence of a persistent biological effect after discontinuation of the study treatment.

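### The plan aims to look for an effect that persists after treatment stops, but the only between-arm efficacy estimates with confidence intervals are at Week 8, the end of treatment

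*SAP*

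**What the plan says.** **The aim.** SAP 3.1 says the secondary outcomes "will include functional assessments to investigate evidence of a persistent biological effect after discontinuation of the study treatment". Protocol section 11 has the same aim and places the off-treatment assessments "at 4 and 24 weeks after cessation of therapy (Week 12 visit and Week 32 visit").

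**The protocol's analysis rules.** Protocol 11.5 provides for descriptive tables of the exploratory efficacy variables and goes on: "at the 0, 4, 8, 12 and 32 weeks timepoints and appropriate inferential tests with 95% confidence limits of the difference between treatments". Protocol 11.5.1 then says: "All variables recorded in the follow-up period will be presented using appropriate descriptive statistics, and no formal statistical testing will be performed". Protocol 8.2 defines follow-up as Weeks 9 to 32, so it includes both off-treatment visits.

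**The SAP's rules.** SAP 8.3 states: "A similar analysis as foreseen for VAS tolerability scores (see section 8.2) will be performed for exploratory efficacy outcomes at Week 8". Each item listed there is a Week 8 change from baseline. The analysis it borrows from SAP 8.2 is an ANCOVA on treatment and baseline value, reporting least-squares means and their difference, both with 95% CIs. SAP 8.1 provides intervals for treatment differences only where 8.2 and 8.3 call for them. SAP 10.7 gives per-arm summaries and changes from baseline at Weeks 12 and 32. In SAP section 12, the efficacy summary tables are marked for repetition in the final analysis, and the matching between-arm analysis tables (14.2-3.3 to 14.2-8.3) are not.

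**The concern.** The visits that can answer the persistence question are the ones without a planned treatment comparison. A Week 8 difference shows the position at the end of dosing and says nothing about what remains afterwards.

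Without a planned estimate, readers of the report will set one arm's mean change beside the other's and judge the gap by eye. The control arm has only 20 patients, so a gap produced by chance could pass for persistence, or an imprecise null result for its absence. Visual field results will be listed and not analysed (SAP 3.6), so the functional evidence on persistence comes down to visual acuity and PhNR.

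There is also a documentation gap. Protocol 11.5 and 11.5.1 pull in different directions for follow-up visits. The SAP settles on Week 8 only, and SAP 3.6, which lists changes and refinements relative to the protocol, does not mention the choice.

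**Working it through.** **1. Which visits bear on the aim.** Treatment stops at Week 8 (protocol 8.2). The later scheduled visits are Week 12 (4 weeks off drug) and Week 32 (24 weeks off drug). BCDVA, OCT and ERG are scheduled at both (protocol section 2).

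**2. Between-arm comparisons planned, per eye.**

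- Week 8: 1 Visual Acuity Score + 1 logMAR + 1 PhNR + 17 RNFL (4 quadrants + 12 clock hours + 1 average) + 9 macular areas + 6 ganglion-cell sectors = 35.
- Week 12: 0.
- Week 32: 0.

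**3. What protocol 11.5 commits to.** The sentence attaches its visit list to the descriptive statistics. The inferential clause follows with no visits of its own, and the synopsis has the same clause with no visit list. Carrying the list over to the inferential clause fits poorly: Week 0 precedes treatment, and BCDVA, OCT and ERG are not scheduled at Week 4. Section 11.5 is therefore ambiguous on Weeks 12 and 32, while 11.5.1 explicitly rules out formal testing there. It does not rule out an estimate with an interval.

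**4. Precision of the missing estimate.** The documents give no SD, effect size or dropout rate, and no formal sample size calculation, so there is no planned figure to reproduce. In units of the ANCOVA residual SD, ignoring the small term for chance baseline imbalance:

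half-width = t(0.975; n1 + n2 − 3) × √(1/n1 + 1/n2)

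The 40:20 split is from the protocol synopsis. The dropout rates are assumptions, applied equally to both arms. No imputation is planned (SAP 8.4.2), so missing patients reduce n directly.

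| Dropout | n1:n2 | t | √(1/n1 + 1/n2) | Half-width (residual SD) |
|---|---|---|---|---|
| 0% | 40:20 | 2.002 | 0.2739 | 0.548 |
| 10% | 36:18 | 2.008 | 0.2887 | 0.580 |
| 20% | 32:16 | 2.014 | 0.3062 | 0.617 |
| 30% | 28:14 | 2.023 | 0.3273 | 0.662 |

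**5. What this means for a visible gap.** With full data, an adjusted gap of 0.3 residual SD has an interval of 0.3 ± 0.548, about −0.25 to 0.85. A gap of 0.5 gives 0.5 ± 0.548, about −0.05 to 1.05. Both include zero. These gaps are illustrations, not forecasts.

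**6. How many intervals the fix adds.** Running all 35 comparisons at both extra visits would bring the total to 3 × 35 = 105 per eye. The short list in the fix has 1 + 1 + 1 + 1 + 6 = 10 per visit, so it adds 2 × 10 = 20 per eye.

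**The case against.** The strongest reply is that the SAP follows the protocol. Section 11.5.1 is the specific rule for follow-up, and where it mentions confidence intervals it means intervals around means or proportions, not differences. A reader might infer from 11.5 that the protocol promises confidence limits of the difference at Weeks 12 and 32 and that the SAP breaks the promise. The documents do not support that: the visit list belongs to the descriptive statistics, and 11.5.1 points the other way. This part of the reply stands in full.

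Other points carry some weight:

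- **A 95% CI is close to a test.** An ANCOVA interval excludes zero exactly when the two-sided p-value is below 0.05. Omitting the p-value and labelling the result descriptive keeps to the wording of 11.5.1, but whether it keeps to the intent is a judgement. The protocol allows such an interval; it does not clearly require one.
- **Readers can derive an interval themselves.** The change-from-baseline tables give n, mean and SD per arm, so an unadjusted interval can be worked out. The baseline-adjusted one used at Week 8 cannot.
- **The outcomes are exploratory.** This is a phase Ib safety study, persistence is not among the synopsis objectives, and the aim is worded for functional assessments. That limits the consequence and makes structural outcomes supporting evidence only.
- **Week 32 is unmasked.** Acuity depends on patient effort, so a difference there is harder to interpret. Week 12 closes the masked follow-up and does not share this weakness.
- **Multiplicity is not adjusted for** (SAP 8.4.5). That argues for a short list, not for reporting no estimate.

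**Conclusion.** The concern holds in limited form. The plan states an aim of looking for a persistent effect, and it provides no between-arm estimate or interval at either visit that could show one. This is a gap between aim and analysis, together with two protocol passages that need reconciling. It is not a departure from the protocol.

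The effect is confined to the secondary, exploratory outcomes; the primary safety and tolerability analyses are untouched. The added intervals would be wide: about 0.55 residual SD either side with complete data, and 0.58 to 0.66 under the assumed 10-30% dropout. They would be unlikely to settle the question, but they would show how little a modest gap between arms means. The multipliers apply to the ANCOVA residual SD, not to the SD of the change. The change is worth making because it is specific and cheap.

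**What to change.** 1. **Reconcile the passages.** State in SAP 3.6 how protocol 11.5 and 11.5.1 are read for follow-up visits, and that between-arm results there are descriptive estimates without tests.
2. **Extend the SAP 8.3 ANCOVA to Weeks 12 and 32 for a short list:** Visual Acuity Score, logMAR and PhNR, with average RNFL thickness and the six ganglion-cell sectors as supporting structural outcomes. Report the least-squares mean difference with its 95% CI, labelled descriptive, with no p-value. Keep the Primary Eye as the main result and the Secondary Eye as supportive, as SAP 8.3 already does.
3. **Place the results.** Put Week 12 in the main-objective analysis and Week 32 in the final analysis, using Tables 14.2-3.3, 14.2-4.3, 14.2-5.3, 14.2-6.3 and 14.2-8.3, and mark these five for repetition in SAP section 12. Leave PanoMap Table 14.2-7.3 as it is.
4. **Add footnotes** saying that Week 32 data come from unmasked follow-up, that the intervals are not adjusted for multiplicity, and how many patients per arm contribute at each visit.

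The cost is one existing model rerun at two visits already scheduled, with no new patients or assessments. The downside is 20 more unadjusted intervals per eye and limited interpretability at Week 32.
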